### 5.7.4. HINT-N

Calculations described for HINT-Q in sections 5.7.1, 5.7.2, 5.7.3, will have to be performed on the HINT-N (refer to tables 13 and 14).

## 5.8. Technical functionalities - Impedance

Average of each electrode impedance at each time points and description of localization and number of electrode deactivation (refer to table 15 and related figure).

## 5.9. Safety data

According to the Protocol, safety data are collected from the pre-operative visit (during surgical procedure) to the end of patient participation.

The number and the percentage of patients who experienced:

- at least one Adverse Event (AE)

- at least one Serious Adverse Event (SAE)
- at least one Adverse Event that led to discontinuation (DisAE): action taken of the AE ticked Discontinued permanently
- at least one Fatal Adverse Event: outcome of the AE ticked Death
- at least one complication
- at least one minor complication

will be calculated (table 16.1).

The total number of events, the mean number of events in patients experiencing the event and the percentage of patients experiencing the event will be reported (table 16.2).

An AE is any adverse change from the subject's baseline condition, symptoms or disease which is considered to be clinically relevant by the investigator that occurs whether or not it is considered to be related to the medical device. A complication is any adverse change symptoms or disease related to the surgery or the medical device

Complications will be classified as major or minor according to the Cohen & Hoffman criteria by the investigator.

Then, MedDRA classification will be performed on all adverse events, during the review of data (refer to table 16.3).

A presentation of all AEs (refer to table 16.4) will be made according to System Organ Class (SOC) and Preferred Term (PT) from MedDRA classification. Incidence rates will be summarized for each PT and SOC terms.

## 6. Statistical analysis

### 6.1. Analysis of efficacy endpoint

The primary analysis of the primary efficacy endpoint will be performed on a subgroup of the FAS which consists of all English-speaking subjects.

Additional analysis with a replicate PPS will be performed on this subset of English-speaking patients.

The primary test is a one sample T-test performed on the change from baseline to 6 months after activation of the device. The value of the mean improvement under the null hypothesis is zero. The type I error ( $\alpha$ ) is set to 0.025 (one-sided).

The one sample Wilcoxon rank test will be applied in a sensitivity analysis. In case the normality assumption is strongly violated or in the presence of several outliers, the result of this sensitivity analysis will have a particular importance.

To further describe the benefit of the Neuro CIS in the studied population, the number of patients (as well as rate among the total population) showing a benefit of at least 20 percentage points in HINT-Q score after 6 months of device use when compared to baseline will be computed (table 8 with the related figure and table 16.6).

## **6.2. Co-primary analysis of safety endpoint**

No formal hypothesis testing of safety data will be performed.

The incidence rate of major complications will be presented as well as its 95% exact confidence interval (CI). A forest plot will present this rate with its 95% CI and the rates with the 95% CI of major complications obtained in previous generation and in the scientific literature (refer to the tables 9.1, 9.2 and the related figure).

## **6.3. Analysis of secondary endpoints**

### **6.3.1. Time course of the HINT-Q response in FAS and PPS**

The analysis will be done on the FAS sub-group of English-speaking patients and replicated in PPS.

The time course of the change from baseline in the HINT-Q will be estimated with a mixed model for repeated measures using the change from baseline as the response, the patients (random effect) and the visit (fixed effect) as covariates.

The time (visit) effect will be tested (H1: at least two visits differ on average) and if a significant effect of visits is observed then visits responsible for the significant difference will be searched.

The intercept and its 95% confidence interval will be interpreted as the coverage effect of the implant over a period of one year. This will be an approximation due to the absence of an assessment at 9 months.

The 95% Confidence Interval of the mean at each visit will be provided.

(refer to table 10)

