##### **a. Description**

The HINT (Hearing in noise Test) was developed at the House Ear Institute (Los Angeles, California) and measures speech recognition thresholds in quiet and noise [3]. When used to determine implant candidacy, the HINT sentences are generally presented in quiet.

The HINT is recognized as a primary assessment instrument for measuring a subject's ability to hear in quiet and in noise. HINT was originally designed as an adaptive speech recognition test based on a correct response of the entire sentence [3]. An intensity level measurement for the sentence speech-reception threshold was determined by presenting random HINT sentences in competing speech-shaped noise (SSN). However, current clinical use of HINT sentences routinely deviates from this original design; instead, HINT sentences are presented in quiet to obtain an accuracy measure, which is important for determining cochlear implant candidacy [4]. Disability evaluation under social security, requires that this testing be conducted in quiet at 60dB SPL [10].

A digital recording is presented to the subject placed inside a sound isolation booth.

For this protocol, subjects shall be tested with two sentence lists

- during inclusion (visit 2)
  - in quiet and in noise in the best aided condition and
- at 3, 6 and 12 months (visits 6, 7 and 8 respectively)
  - in quiet and
  - in noise condition in the ipsilateral electrically stimulated ear with an occluded contralateral ear.

The noise and/or the signal shall be presented from the front of the recipient at 0° azimuth

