## **3.6 Study Outcome Evaluations**

### **3.6.1 Study Endpoints**

#### **3.6.1.1 Primary Endpoints**

Previous studies analyzed their samples based on fixed time intervals after implantation, usually 1, 3 and 6 months, then annually thereafter. After 6 months of CI experience outcomes appear to be stable with the majority of users reaching a performance plateau. Massa et al. [5] observed a performance plateau at a median of 4.7 months post-implantation. Similar results were reported by Bradley et al. [8] demonstrated a plateaued performance around 6 months in a sample of 55 patients. In Dillon et al. study [9] the adults tested with HINT in quiet at 70 dB experienced growth in speech perception within the first 6 months and remained stable thereafter. This plateau at 6

months is generally consistent with findings from others previous research with other speech discrimination tools, as Lenarz et al. study [7] using German language tests in a large cohort.

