## 5. Data analysis

All statistical analysis will be generated using SAS version 9.4.

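### SAP 6.3.1 reads the mixed-model intercept as a one-year implant effect, but no categorical coding of visit makes it one, and the coding is not stated

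*SAP*

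**What the plan says.** SAP 6.3.1 specifies a mixed model for repeated measures in the English-speaking FAS subgroup, repeated in the PPS, "using the change from baseline as the response, the patients (random effect) and the visit (fixed effect) as covariates". The visit effect is tested against the alternative "H1: at least two visits differ on average", which implies a categorical visit with three levels. Two interpretive sentences follow: "The intercept and its 95% confidence interval will be interpreted as the coverage effect of the implant over a period of one year" and "This will be an approximation due to the absence of an assessment at 9 months". The section then adds: "The 95% Confidence Interval of the mean at each visit will be provided".

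No coding or reference level for visit is given. SAP section 5 says only "All statistical analysis will be generated using SAS version 9.4", which names neither a procedure nor a parameterisation. The shell for Table 10, to which 6.3.1 refers, has no cell for an intercept or its interval.

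Protocol 3.5.5.1 schedules the postoperative HINT tests "at 3, 6 and 12 months (visits 6, 7 and 8 respectively", with one preoperative test at visit 2. Protocol 3.6.2.4 a) describes the same model but says nothing about the intercept and has no month-9 caveat.

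**The concern.** An intercept has no meaning until the coding of the other terms is fixed. Here two analysts could follow the SAP faithfully, report different numbers, and attach the same one-year label to both.

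The label also claims more than the schedule can support. Protocol 3.6.1.1 describes scores as still growing during the first six months, and one study cited there "observed a performance plateau at a median of 4.7 months post-implantation". The first postoperative test (visit 6) falls 105 to 118 days after surgery by Protocol 3.5.6. That is about 3.5 to 3.9 months, so roughly a month before that median. The steepest part of the first year is therefore likely to lie where the trial takes no measurement, and the caveat does not mention it.

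At stake is one supportive summary with a confidence interval that does not target the quantity named.

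**Working it through.** **Plan's own figures.** The SAP gives no number for the intercept, so there is none to reproduce. The planning inputs used below come from the efficacy sample size in SAP 1.3 (mean 50, SD 25, one-sided 0.025, 95% power, 7 patients). The exact noncentral t gives power 97.1% at n = 6 and 99.1% at n = 7, so the stated 7 is adequate.

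**Inputs (SAP 1.3).** Mean change of 47.7 at 3 months (a cited study, counted from implantation), 50 at 6 months (planning value), and 60 at 12 months (another cited study). These are illustrative because they come from different sources. Two flatter courses are also shown: 47.7/50/50, and 47.7/57.43/57.43 using the pooled literature value.

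**Step 1: what the intercept is.** Write m3, m6 and m12 for the mean changes.
- Reference coding: the intercept is the mean at the reference visit, so m3, m6 or m12.
- Sum-to-zero coding: (m3 + m6 + m12)/3 = (47.7 + 50 + 60)/3 = 52.6.

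Any categorical coding gives a combination of these three means. None of them carries information about activation to M3.

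**Step 2: a one-year average for comparison.** The trapezoid rule on months 0, 3, 6 and 12 after activation needs a change c0 at activation, which the documents do not give:

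[3(c0 + m3)/2 + 3(m3 + m6)/2 + 6(m6 + m12)/2]/12

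For 47.7/50/60:
- c0 = 0: (71.55 + 146.55 + 330)/12 = 45.7
- c0 = 47.7 (full M3 gain already present): (143.1 + 146.55 + 330)/12 = 51.6
- c0 = -14 (loss of the 14% mean baseline score in one study cited in Protocol 2.1): (50.55 + 146.55 + 330)/12 = 43.9

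**Step 3: intercept minus one-year average, in points.**

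| Course M3/M6/M12 | c0 | Year average | M3 ref. | M6 ref. | M12 ref. | Sum-to-zero |
|---|---|---|---|---|---|---|
| 47.7/50/60 | 0 | 45.7 | +2.0 | +4.3 | +14.3 | +6.9 |
| 47.7/50/60 | 47.7 | 51.6 | -3.9 | -1.6 | +8.4 | +0.9 |
| 47.7/50/50 | 0 | 43.2 | +4.5 | +6.8 | +6.8 | +6.1 |
| 47.7/50/50 | 47.7 | 49.1 | -1.4 | +0.9 | +0.9 | +0.1 |
| 47.7/57.43/57.43 | 0 | 47.8 | -0.1 | +9.6 | +9.6 | +6.4 |
| 47.7/57.43/57.43 | 47.7 | 53.8 | -6.1 | +3.6 | +3.6 | +0.4 |

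With c0 = -14, the sum-to-zero error is +7.8 to +8.6 across the three courses.

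**Step 4: the month-9 caveat.** Interpolating month 9 as (50 + 60)/2 = 55 gives a four-visit mean of (47.7 + 50 + 55 + 60)/4 = 53.2, against 52.6 without it. The shift is 0.6 points (0.2 and 0.8 in the other two courses). The untested start moves the year average by 51.6 - 45.7 = 5.9 points between c0 = 47.7 and c0 = 0.

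**Step 5: interval coverage.** In 300 simulated trials (n = 39, SD 25, assumed within-patient correlation 0.7, course 47.7/50/60, c0 = 0), the nominal 95% interval for the intercept contained 45.7 in about 5% of trials with M12 reference, 53% with sum-to-zero and 91% with M3 reference coding.

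**The case against.** The SAP already calls its reading an approximation and states no number. The month-9 remark makes most sense if the author meant a plain average over visits that would have been evenly spaced at 3, 6, 9 and 12 months. On that reading the intercept is 52.6, close to the time-weighted M3-to-M12 mean of 52.95, and what remains is the label and the untested start. The analysis is also supportive: Protocol 3.6.2.4 rests labelling claims on the primary analysis alone. The changes at M3, M6 and M12 appear in SAP Tables 8 and 11.1 anyway. All of this stands and limits the importance of the point. It does not repair the sentence, since the intended coding is not written down and the caveat names the smaller gap.

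Three stronger readings are tempting and are not supported.
- **The reported effect will be too high.** That is so with M12-reference or sum-to-zero coding in the courses tabulated, if scores rise from near zero at activation. M3-reference coding can err the other way: with an assumed slow start of 25/50/50 and c0 = 0, the year average is 37.5 and the M3-reference intercept is 12.5 points below it.
- **The software settles the coding.** The SAP names SAS 9.4 but no procedure or reference level.
- **There is no speech test before month 3.** There is a preoperative test at visit 2; what is missing is a postoperative one. The SAP 1.4 grid, as extracted, marks HINT at V5 to V7, but Protocol 3.5.5.4 and SAP 2.1 place it at V6 to V8. The grid should be checked, though the shift may be an artefact of extraction.

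**Conclusion.** The point holds as a minor correction to a supportive analysis. Under either standard categorical coding the intercept is not a one-year average, and the SAP leaves the coding open. On the documents' values the choice alone spans 47.7 to 60.0, or 12.3 points. If the course is flat after month 6 at 50, the span shrinks to 2.3 points (47.7 to 50.0).

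The distance from a true one-year average cannot be determined from the trial, because it rests on an assumed value at activation. Over the six rows tabulated it runs from -6.1 to +14.3 points, so neither a size nor a sign should be asserted. The primary M6 t-test and the per-visit means with their intervals are not affected.

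**What to change.** Delete the intercept sentence and the month-9 caveat from SAP 6.3.1. This brings it back into line with Protocol 3.6.2.4 a), which has neither. SAP 6.3.4 repeats the HINT-Q analyses for HINT-N, so the deletion should carry over there.

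If a single summary is wanted, define it as a contrast of the visit least-squares means with its 95% CI, so that it no longer depends on coding. One option is the time-weighted mean with weights 1/6 (M3), 1/2 (M6) and 1/3 (M12), from 1.5/9, 4.5/9 and 3/9. In the worked example this is 47.7/6 + 50/2 + 60/3 = 52.95. A stated equal-weight mean would also serve. The gain is a defined quantity and an honest label: 52.95 is slightly above the sum-to-zero 52.6, so the contrast does not remove the gap to a one-year average.

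Label it as the average effect from the M3 to the M12 visit, and state that activation to M3 was not measured and that no one-year average is claimed. Naming visits is safer than naming months of use. Protocol 3.5.6 puts visit 8 at 357 to 370 days and activation at 25 to 34 days after surgery, so about 11 months of use, while the schedule in 3.5.5.4 says month 13 after surgery. The weights are the same either way, because the nominal spacing from activation is 12, 24 and 48 weeks or 3, 6 and 12 months.

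The cost is one SAP paragraph, one contrast statement and a row in Table 10, with no new data. The drawback is that the summary no longer covers the full first year.

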### **6.3.2. Sustainability of the effect at 12 months in FAS and PPS**

HINT-Q performed at Month 6 in the FAS and PPS sub-group of English speaking patients will be compared to the result at Month 3, and the result at month 12 will also be compared to those obtained at Month 3 and 6 to assess the sustainability of the effect over time.

A one-sided ( $\alpha = 0.025$ ) t-test for paired samples will be used. (refer to tables 11.1 and table 11.2).

### **6.3.3. Homogeneity of HINT-Q results across languages and estimates of effects in the FAS and PPS**

(Refer to table 12)

This analysis will be done on the FAS and replicated in PPS.

A mixed model for repeated measures will be fitted using the change from baseline to Month 3, Month 6 and Month 12 in the HINT-Q score as the responses and the following covariates or terms: the visit (M3, M6 and M12, fixed effect), the patient (random effect), the language (fixed effect) and the interaction between visit and language. The variance covariance matrix will be unstructured.

If the p value of the interaction is below 0.15 then a signal of potential interaction will be detected and the time course of the change from baseline will be possibly dependent upon the language.

If the p value of interaction is above 0.15, an interaction will be still possible due to the poor power of the interaction test, but the magnitude of the difference should be limited. Findings obtained on the three languages combined will provide a better external validity than those obtained on English speaking only. Consequently, the interaction will be interpreted as a measure of the generalizability of the effect across languages.

Regardless the p value of interaction a graph will present the time course of the response for each language and for all languages combined.

A series of contrasts will be performed to estimate and test (table 12):

- The difference between languages in the magnitude of the change from baseline at each time point. The contrast at Month 6 will be of major importance.
- The magnitude of the change from baseline to each time point for the 3 languages combined. The estimate at Month 6 will be the most supportive result.
- The significance (difference from zero) of overall (all languages) change at each time point.
- The overall difference between Month 6 and Month 12 of the change from baseline (all languages combined).
- The visit effect (is there a difference between visits in the change from baseline?)
- In the presence of potential interaction between languages and time then the mean effect of languages will be investigated.

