**c) Difference in the time course of HINT-Q responses across languages**

The FAS including all patients instead of the subset of English speaking patients will be used in these secondary analyses. A mixed model for repeated measures will be fitted using the change from baseline to M3, M6 and M12 in the HINT-Q score as the responses and the following covariates or terms: the visit (M3, M6 and M12, fixed effect), the patient (random effect), the language (fixed effect) and the interaction between visit and language. The variance covariance matrix will be unstructured. If the p value of the interaction is below 0.15 then a signal of potential interaction is detected and the time course of speech performance is possibly dependent upon the language. Regardless the p value of interaction a graph will present the time course of the response for each language.

A series of contrasts will be performed to estimate and test:

1) The difference between languages in the change from baseline at each time point.

The estimate and test at M6 will be the most supportive result.

2) The overall mean change from baseline at each time point. The test against no change will be performed. Results will be easily interpreted in the absence of potential interaction (No significant difference in the time course of response between the 3 languages).

3) The overall difference between M6 and M12 in the change from baseline to assess the sustainability of effect in the overall population. This estimate is interpretable in the absence of interaction between visit and language. In the presence of interaction the difference is not easily interpretable and sustainability will be estimated and tested in the English speaking patients only.

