### 1.3. Determination of sample size

Sample size determination is based on the two co-primary endpoints: change from baseline to 6 months of the HINT-Q (efficacy assessment), and major complication incidence rate during the 12-month follow-up (safety assessment).

The expected efficacy is an improvement of 50 points at 6 months of device use.

Data on the change from baseline to 6 months are not available in literature, but 2 studies describe the HINT-Q magnitude after 12 months of device use. Waltzman et al. [1] described an increase of 47.7% (SD=26.6%) from pre- to 3 months post-implantation, similar results are reported by Lin et al. [2] with a magnitude of 60% (SD=24.1%) at 12 months. Considering an observed performance plateau around 6 months, we can consider that standard deviation obtained at 3 and 12 months can be used for 6 months of device use in this study. In addition, in the main studies conducted at 6 months, the standard deviation are ranged from 22% to 28%, which is consistent with other results on the change from baseline. Data from literature using the same efficacy assessment criterion provided a weighted average  $\pm$  weighted standard deviation change from baseline of 57.43%  $\pm$  25.05%. Such estimation has been rounded conservatively to 50%  $\pm$  25%.

The sample size required to have 95% chance to get a significant efficacy result assuming a true mean improvement of 50%, a standard deviation of change from baseline of 25% and a type I error of 0.025 (one-sided) is 7 patients. It means that the expected improvement is so large with respect to the variability that the sample size calculation is not driven by efficacy considerations.

As requested by the FDA, the sample size will be set at a total of at least 50 subjects to support the safety. If the incidence rate of major complications is 2% then the chance to observe at least one event is 63.5%. The exact upper limit of the 95% CI will be 10.6% for an observed rate of 2%.

Regarding any complication the expected rate 35%. If the observed rate is 36% then the precision is around 13% in points.

In order to ensure that at least 50 subjects will be implanted with the device, starting with the anesthesia followed by surgery procedure, 55 subjects will be included.

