## 6.5. Site effects analysis

The site effect is partly confounded with the language effect. Consequently, the site effect will be investigated in English speaking patients. An analysis of variance using the change from baseline to M6 as the response and the site as covariate will be performed. If the site effect is significant, then the mean change from baseline to M6 is dependent upon the site. Regardless the p value of ANOVA a Forest plot presenting the mean change from baseline to M6 of each site along with the 95% confidence interval will be presented to verify whether there is just a quantitative difference across sites or a qualitative one (refer to table 12 and the related figure). In case of significant site effect and qualitative difference the site with the largest mean deviation from the overall mean change from baseline will be removed from the sample to estimate the overall mean change from baseline in the remaining sites.

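### The by-visit language contrasts and the site ANOVA of HINT-Q change omit baseline HINT-Q, so a baseline gap between groups carries into the language or site effect

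*SAP*

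**What the plan says.** - **Language model.** SAP 6.3.3 fits a mixed model "using the change from baseline to Month 3, Month 6 and Month 12" in HINT-Q as responses. Its terms are visit, patient and, as in Protocol 3.6.2.4 c, "the language (fixed effect) and the interaction between visit and language". The model block of mock Table 12 lists patient, visit and language only.
- **Weight given to it.** Of the between-language differences at each visit, the SAP says "The contrast at Month 6 will be of major importance". On the visit-by-language term it says "If the p value of the interaction is below 0.15 then a signal of potential interaction will be detected".
- **Language gate.** SAP 1.2 and 5.7.3 extend the sustainability analysis to all patients only if there is no language effect. Otherwise it stays with the English speakers.
- **Site model.** In SAP 6.5 (and Protocol 3.6.2.4 h), "An analysis of variance using the change from baseline to M6 as the response and the site as covariate will be performed", in English speakers only, because "The site effect is partly confounded with the language effect". If the site effect is significant and the difference is qualitative, "the site with the largest mean deviation from the overall mean change from baseline will be removed from the sample" and the mean is re-estimated in the remaining sites.
- **Baseline.** HINT-Q is recorded at visit 2. It is a covariate in none of these models, and no sensitivity analysis adds it. Table 12 shows it by language descriptively. It is not tabulated by site.

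**The concern.** HINT-Q is a 0-100% score and entry requires 50% or less, so the largest possible gain runs from 50 to 100 points depending on where a patient starts. If change depends on baseline, two groups that start at different levels will show different mean changes even when they do equally well at a given starting score. With 8 patients planned per non-English language, and as few as 5 allowed, such gaps can arise by chance. Languages and sites are also not randomised, so systematic gaps are possible.

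The results feed two decisions: which population enters the sustainability analysis, and whether a site is dropped for a re-estimate.

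**Working it through.** **1. The plan's own figure.** SAP 1.3 sizes efficacy "assuming a true mean improvement of 50" percentage points, with a change SD of 25, one-sided alpha 0.025 and 95% power, and states 7 patients. Exact one-sample t-test power at effect 50/25 = 2 is 90.9% for n = 5, 97.1% for n = 6 and 99.1% for n = 7. Seven is sufficient. The documents give no power or precision figure for the language or site comparisons.

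**2. Inputs.** From the documents: change SD 25 and 6-month score SDs of 22 to 28 (SAP 1.3); 39 English, 8 Danish and 8 French (Protocol 1), with minimum 5 and 5 (SAP 1.3). Assumed: baseline SD 15 to 17. Of the two pre/post series cited in Protocol 2.1, one has baseline SD 17 (mean 14). The other has 25.6 (mean 11.3), but scores confined to 0-50 with that mean can have an SD of at most sqrt(11.3 × 38.7) = 20.9.

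**3. Formulas.** With s0 and s6 the baseline and Month 6 SDs:
- r = (s0² + s6² − 25²) / (2·s0·s6)
- slope of change on baseline = r·s6/s0 − 1
- residual SD after adjustment = s6·sqrt(1 − r²), compared with 25 unadjusted

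| s0 / s6 | r | slope | residual SD | SE ratio |
|---|---|---|---|---|
| 15 / 22 | 0.13 | −0.81 | 21.8 | 0.873 |
| 15 / 25 | 0.30 | −0.50 | 23.8 | 0.954 |
| 15 / 28 | 0.46 | −0.15 | 24.9 | 0.996 |
| 17 / 22 | 0.20 | −0.74 | 21.6 | 0.863 |
| 17 / 25 | 0.34 | −0.50 | 23.5 | 0.940 |
| 17 / 28 | 0.47 | −0.22 | 24.7 | 0.988 |

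**4. Carry-over.** A 10-point gap times the slope gives 1.5 to 8.1 points, 5 in the 15/25 case. The slope is sensitive to the assumed baseline SD: at s0 = 10 it runs from −1.21 (s6 = 22) to +0.30 (s6 = 28).

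**5. Chance of a 10-point gap.** The SE of the baseline gap is s0·sqrt(1/39 + 1/n).
- n = 8: 15 × 0.388 = 5.8 and 17 × 0.388 = 6.6, so the two-sided probability of exceeding 10 points is 9% to 13%.
- n = 5: 15 × 0.475 = 7.1 and 17 × 0.475 = 8.1, giving 16% to 22%.

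**6. Precision.** For 39 v 8 at one visit, in the 15/25 case, the SE falls from 25 × 0.388 = 9.7 to 9.3, and the 95% half-width from 19.5 to 18.6 points. Imbalance gives some of this back: a gap of D baseline SDs inflates the adjusted variance by 1 + D²/[52 × (1/39 + 1/8)], which is 1.03 at D = 0.5. At 17/28 the variance ratio 0.98 × 1.03 is about 1.01, so nothing is gained.

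**7. Site ANOVA.** Simulation with 3,000 runs per setting, four assumed English-speaking sites of 10, 10, 10 and 9, normal scores, and one site shifted in baseline only. The SD pairs were 15/25, 17/28 and 15/22. At nominal 5%, the planned ANOVA rejects in 5% to 8% of runs for a 10-point shift and 6% to 24% for a 20-point shift. With baseline in the model it rejects in about 5%.

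**8. What does not move.** In (M12 − baseline) − (M6 − baseline) the baseline cancels. Within-patient visit contrasts and the visit-by-language test are therefore unchanged by a baseline term whose slope is common to all visits.

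**The case against.** The strongest objection concerns the target. The SAP asks how the magnitude of change differs between languages, and the unadjusted contrast estimates exactly that. The groups are not randomised, each language has its own HINT lists (Protocol 3.5.5.1), and the test software depends on language (Appendix 9). An equal starting score is therefore not clearly an equal starting level. A linear term may also fit poorly: Appendix 7 records 0 after early stopping, so a cluster at 0 is likely. All of this stands, and it is why the adjusted model should sit beside the planned one and not replace it.

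The consequences are also limited. Protocol 3.6.2.4 calls these analyses supportive and rests labelling claims on the primary analysis alone. Table 12 would already show a baseline gap between languages, though nothing shows one between sites.

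Three stronger readings are tempting, and the documents do not support them.
- *Adjustment buys a large gain in precision.* The cited pair 25.6/24.9 gives a residual SD of 21.4, an SE 14% lower, but a baseline SD of 25.6 at that mean is impossible under the 50% entry ceiling. A similar figure arises here only at the 17/22 corner of the assumed grid.
- *Every contrast is distorted.* Step 8 shows otherwise. Protocol 3.6.2.4 c ties the pooled sustainability estimate to the interaction, so the gate is exposed only if it is read, as SAP 1.2 words it, on the language effect in improvement.
- *A baseline gap alone could get a site removed.* Removal also needs a qualitative difference. Even a 20-point gap at slope −0.81 moves a site mean by about 16 points, against an expected gain of 50.

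**Conclusion.** The point holds for the between-language contrasts at a given visit and for the Month 6 site ANOVA. Under baseline SD 15 to 17, Month 6 SD 22 to 28 and change SD 25, a 10-point baseline gap shifts the contrast by about 2 to 8 points, central 5. That is smaller than the planned contrast's half-width of about 19 points, but it is systematic, and the adjusted model would show it. Carry-over is the main issue. The precision gain is secondary: about 5% of the SE centrally, range about 0-14%, and partly lost if groups are imbalanced.

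The primary one-sample t-test is untouched. This is a low-severity improvement. The baseline SD, the number and size of English-speaking sites, and normality of scores are assumptions, and the cited SDs come from different studies, so the correlations are illustrative.

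**What to change.** - **SAP 6.3.3.** Keep the planned model. Beside it, report the language contrasts at each visit with baseline HINT-Q and baseline-by-visit as covariates.
- **SAP 6.5.** Keep the planned ANOVA. Beside it, report the site comparison with baseline HINT-Q as a covariate, and tabulate baseline by site.
- **Decisions.** State that both versions are read before the language gate (SAP 1.2, 5.7.3) or the site-removal rule (SAP 6.5) is applied, and name the test that defines the gate.
- **HINT-N.** First reconcile SAP 6.3.4, which takes the post-implantation score as response, with Protocol 3.6.2.4 d, which takes change from baseline. Then add baseline HINT-N in the same way. With baseline and baseline-by-visit in the model, the group contrast at each visit is the same under either response.

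The cost is a few SAP lines and extra rows in Tables 12 and 14, with no new data. The downside is interpretive: the adjusted contrast means at equal starting score, measured on language-specific lists, and does not remove confounding. With 5 to 8 patients per non-English language, the added terms should be kept to these.
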